5.1 Definitions

An AE is defined as any untoward medical occurrence in a patient or clinical trial subject administered a medicinal product and which does not necessarily have a causal relationship with this treatment. Adverse events would not include information recorded as medical history at screening for preplanned procedures for which the underlying condition was known and no worsening occurred. An adverse reaction is any untoward and unintended response to an IMP related to any dose administered.

A suspected adverse reaction is any AE for which there is a reasonable possibility that the IMP caused the AE. For the purpose of Investigational New Drug (IND) safety reporting, "reasonable possibility" means there is evidence to suggest a causal relationship between the IMP and the AE. Suspected adverse reaction implies a lesser degree of certainty about causality.

An SAE includes any event that results in any of the following outcomes:

- Death
- Life-threatening; ie, the subject was, in the opinion of the investigator, at immediate risk of death from the event as it occurred. It does not include an event that, had it occurred in a more severe form, might have caused death.
- Persistent or significant incapacity/disability or substantial disruption of the ability to conduct normal life functions.
- Requires in-patient hospitalization or prolongs hospitalization.
 - Hospitalization itself should not be reported as an SAE; whenever possible the reason for the hospitalization should be reported.
 - Hospitalizations or prolonged hospitalizations for social admissions (ie, those required for reasons of convenience or other non-medical need) are not considered SAEs.
- Congenital anomaly/birth defect.
- Other medically significant events that, based upon appropriate medical judgment, may jeopardize the subject and may require medical or surgical intervention to prevent one of the outcomes listed above; eg, allergic bronchospasm requiring intensive treatment in an emergency room or home, blood dyscrasias or convulsions that do not result in hospitalization, or the development of drug dependency or drug abuse.

Nonserious adverse events are all AEs that do not meet the criteria for a "serious" AE.

Protocol 405-201-00013

Immediately Reportable Event (IRE):

- Any SAE.
- Any AESI (see [Section 5.4](#)).
- Any AE related to occupational exposure.
- Potential serious hepatotoxicity (see [Section 5.6](#)).
- Pregnancies are also defined as IREs. Although normal pregnancy is not an AE, it will mandate IMP discontinuation and must be reported on an IRE form to the sponsor. Pregnancy will only be documented on the AE eCRF if there is an abnormality or complication.

Clinical Laboratory Test Value Changes: It is the investigator's responsibility to review the results of all laboratory tests as they become available. This review will be documented by the investigator's dated signature on the laboratory report. For each abnormal laboratory test result, the investigator needs to ascertain if this is an abnormal (ie, clinically significant) change from baseline for that individual subject. This determination, however, does not necessarily need to be made the first time an abnormal value is observed. The investigator may repeat the laboratory test or request additional tests to verify the results of the original laboratory tests. If this laboratory value is considered medically relevant by the investigator (subject is symptomatic, requiring corrective treatment or further evaluation), or if the laboratory value leads to discontinuation, or fulfills a seriousness criterion, this is considered an AE.

Severity: Adverse events will be graded on a 3-point scale and reported as indicated on the eCRF. The intensity of an adverse experience is defined as follows:

- 1 = Mild:** Discomfort noticed, but no disruption to daily activity.
- 2 = Moderate:** Discomfort sufficient to reduce or affect normal daily activity.
- 3 = Severe:** Inability to work or perform normal daily activity.

IMP Causality: Assessment of causal relationship of an AE to the use of the IMP is defined as follows:

- Related:** There is a reasonable possibility of a temporal and causal relationship between the IMP and the AE.
- Not Related:** There is no temporal or causal relationship between the IMP and the AE.

Protocol 405-201-00013

5.2 Eliciting and Reporting Adverse Events

The investigator will periodically assess subjects for the occurrence of AEs. To avoid bias in eliciting AEs, subjects should be asked the non-leading question: “How have you felt since your last visit?” All AEs (serious and nonserious) reported by the subject must be recorded on the source documents and eCRF provided by the sponsor. Serious AE collection is to begin after a subject has signed the eICF.

Use medical terminology in AE reporting. Adverse events should be reported as a single unifying diagnosis whenever possible or, in the absence of a unifying diagnosis, as individual signs or symptoms. Exacerbation or disease progression should be reported as an AE only if there are unusual or severe clinical features that were not present, or experienced earlier, or not expected based on the course of the condition.

In addition, the sponsor must be notified immediately by telephone, fax, or e-mail of any IREs according to the procedure outlined below, in [Section 5.3](#). Special attention should be paid to recording hospitalization and concomitant medications.

5.3 Immediately Reportable Events

The investigator must immediately report after either the investigator or site personnel become aware of any SAE, AE related to occupational exposure, AESI, potential serious hepatotoxicity, or confirmed pregnancy, by telephone, fax, or e-mail to the sponsor or designee using the contact information on the cover page of this protocol. An IRE form must be completed and sent by e-mail, fax, or overnight courier to the sponsor or designee. (Please note that the IRE form is NOT the AE eCRF.)

Subjects experiencing SAEs should be followed clinically until their health has returned to baseline status, or until all parameters have returned to normal or have otherwise been explained. It is expected that the investigator will provide or arrange appropriate supportive care for the subject and will provide prompt updates on the subject’s status to the sponsor or designee.

5.4 Adverse Events of Special Interest

Newly acquired skin eruptions that are non-traumatic will be considered AESIs. These may include, but are not limited to eruptions such as skin rashes, skin irritations, skin reactions, or acneiform lesions. This does not include localized contact irritation at ECG lead sites due to application or removal of lead adhesive.

Protocol 405-201-00013

Refer to the separate rash workup plan for complete details, including reporting forms, and extra measures that must be performed to characterize any skin AESI of a newly acquired skin eruption that is non-traumatic. The trial site will have a local designated dermatologist available for immediate consultation during the trial for these AESIs.

All AESIs should be reported as IREs ([Section 5.3](#)).

5.5 Abuse Potential Monitoring Plan, Events Subject to Additional Monitoring, and Medication Handling Irregularities

A key objective of the Abuse Potential Monitoring Plan (APMP) is to monitor for instances of abuse or diversion of the trial medication and other psychoactive substances. In addition to monitoring for irregularities in medication handling, AEs that may be suggestive of a developing abuse issue will also receive special attention. As part of the APMP, medication handling irregularities (MHIs) must be reported, and AEs related to abuse potential and AEs involving MHIs must be reported as Events Subject to Additional Monitoring (ESAMs) with detailed narratives.

Investigators and site staff at each trial site will be trained on reporting potentially abuse-related AEs (eg, recording a description of the event in the subject's own words in the source documents as well as the eCRF, in addition to the clinical term, and to be aware that a subject's report may encompass more than one event and that these should be recorded separately). The investigators will be provided with examples of potentially abuse-related AEs, and trained on how to handle such events (eg, additional monitoring). While the investigators will be provided with examples of AE terms as a guide during trial conduct, the analysis of potentially abuse-related AEs will be based on a search of all Medical Dictionary for Regulatory Activities (MedDRA) preferred terms, all verbatim terms, and any open text fields within the AE data to identify text strings suggestive of abuse potential, in line with the 2017 FDA guidance (Assessment of Abuse Potential of Drugs).⁴⁰ Refer to the separate APMP documentation for complete details on MHIs and ESAMs, including documenting and reporting procedures, examples of potentially abuse-related AE terms that meet the criteria for ESAM reporting, and guidance for the training of investigators and trial site staff.

5.6 Potential Serious Hepatotoxicity

For a subject who experiences an elevation in aspartate aminotransferase (AST) or alanine aminotransferase (ALT) that is ≥ 3 times the upper limit of normal (ULN), a total bilirubin level should also be evaluated. If the total bilirubin is ≥ 2 times the ULN, complete an IRE form with all values listed and also report as an AE on the eCRF.

Protocol 405-201-00013

5.7 Pregnancy

Females of childbearing potential are defined as female subjects for whom menstruation has started and who are not documented as sterile (ie, have had a bilateral oophorectomy or hysterectomy or who have been postmenopausal for at least 12 consecutive months).

For FOCBP and for males who are sexually active, there must be a documented agreement that the subject and their partner will take effective measures (ie, double-barrier method) to prevent pregnancy during the course of the trial and for 30 days after the last dose of IMP for female subjects, and 90 days after the last dose of IMP for male subjects and their partners who are FOCBP. Unless the subject is sterile (ie, women who have had a bilateral oophorectomy or hysterectomy or who have been postmenopausal for at least 12 consecutive months; or men who have had a bilateral orchidectomy) or remains abstinent, 2 of the following precautions must be used: vasectomy, tubal ligation, vaginal diaphragm, intrauterine device, birth control pills, birth control injection, birth control implant, birth control patch, condom with spermicide, or sponge with spermicide. Any single method of birth control, including vasectomy and tubal ligation, may fail, leading to pregnancy. The contraceptive method will be documented at each trial visit. Male subjects must also agree not to donate sperm from screening through 90 days after the last dose of IMP.

Before enrolling FOCBP in this clinical trial, investigators must review the below guidelines about trial participation with all FOCBP. The topics should generally include:

- General information
- Informed consent form
- Pregnancy prevention information
- Drug interactions with hormonal contraceptives
- Contraceptives in current use
- Guidelines for the follow-up of a reported pregnancy

Before trial enrollment, FOCBP must be advised of the importance of avoiding pregnancy during trial participation and the potential risk factors for an unintentional pregnancy. The subject must sign an informed consent form stating that the above-mentioned risk factors and the consequences were discussed with her.

A urine or serum pregnancy test for human chorionic gonadotropin will be performed at screening on all subjects that are FOCBP. If a urine test is performed and is positive, the investigator will follow up with a confirmatory serum test.

Protocol 405-201-00013

During the trial, all FOCBP should be instructed to contact the investigator immediately if they suspect they might be pregnant (eg, missed or late menstrual cycle).

If a subject is suspected to be pregnant before she receives IMP, the IMP administration must be withheld until the results of serum pregnancy tests are available. If the pregnancy is confirmed, the subject must not receive the IMP and must not be enrolled in the trial. If pregnancy is suspected while the subject is taking IMP, the IMP must be withheld immediately (if reasonable, taking into consideration any potential withdrawal risks) until the result of the pregnancy test is known. If pregnancy is confirmed, the IMP will be permanently discontinued in an appropriate manner (eg, dose tapering if necessary for subject safety) and the subject will be withdrawn from the trial.

The investigator must immediately notify the sponsor of any pregnancy associated with IMP exposure during the trial and for 30 days after the last dose of IMP for female subjects, and for 90 days after the last dose of IMP for partners of male subjects, and record the event on the IRE form and forward it to the sponsor. The sponsor will forward Pregnancy Surveillance Form(s) for monitoring the outcome of the pregnancy.

Protocol-required procedures for trial discontinuation and follow-up must be performed on the subject unless contraindicated by pregnancy (eg, x-ray studies). Other appropriate pregnancy follow-up procedures should be considered, if indicated. In addition, the investigator must report to the sponsor, on appropriate Pregnancy Surveillance Form(s), follow-up information regarding the course of the pregnancy, including perinatal and neonatal outcome. Infants will be followed for a minimum of 6 months from the date of birth.

5.8 Procedure for Breaking the Blind

The investigator is encouraged to contact the sponsor/clinical research organization (CRO) medical monitor to discuss their rationale for unblinding. However, to prevent delays to the investigator or medical personnel responding to a potentially emergent situation, unblinding of IMP will not be dependent upon the investigator receiving approval from the sponsor/CRO medical advisor (ie, the investigator will be able to obtain the code break information independent of the sponsor/CRO medical advisor). The investigator must contact the sponsor/CRO medical advisor by telephone or e-mail with an explanation of the need for opening the treatment assignment code within 24 hours of opening the code. If the blind is broken, the Clinical Safety and Pharmacovigilance department must be notified immediately (see the cover page of this protocol for contact information). Documentation of breaking the blind should be recorded in the subject's medical record with the date and time the blind was broken and the names of the

Protocol 405-201-00013

personnel involved. Once the blind is broken for a subject, that subject may not reinstate treatment with the IMP.

5.9 Follow-up of Adverse Events

5.9.1 Follow-up of Nonserious Adverse Events

Nonserious AEs that are identified at any time during the trial must be recorded on the AE eCRF with the current status (ongoing or resolved/recovered) noted. All nonserious events (that are not IREs) that are ongoing at the last scheduled contact will be recorded as ongoing on the eCRF. For any AE having been identified throughout the trial, during analysis, additional relevant medical history information may be requested by the sponsor to further ascertain causality (including, but not limited to, information such as risk-related behavior, family history and occupation).

5.9.2 Follow-up of Serious Adverse Events and Immediately Reportable Events

This trial requires that subjects that complete the trial be actively monitored for SAEs and IREs up to 7 days after the last dose of IMP is administered. Subjects that decide to not enroll in Trial 405-201-00015, or for subjects that do not complete Trial 405-201-00013, will be actively monitored for SAEs and IREs up to 10 days after the last dose of IMP is administered.

Serious AEs and nonserious IREs that are **identified or ongoing at the last scheduled contact** must be recorded as such on the AE eCRF page. If updated information (eg, resolved status) on SAE or IRE status becomes available after a subject's last scheduled contact (up to last in-clinic visit for the entire trial), this must be reported to the sponsor according to the appropriate reporting procedures. The investigator will follow SAEs until the events are resolved, stabilized, or the subject is lost to follow-up or has died. Resolution means that the subject has returned to the baseline state of health and stabilized means that the investigator does not expect any further improvement or worsening of the subject's condition. The investigator will continue to report any significant follow-up information to the sponsor up to the point the event has resolved or stabilized, or the subject is lost to follow-up, or has died.

Protocol 405-201-00013

5.9.3 Follow-up and Reporting of Serious Adverse Events and Immediately Reportable Events Occurring after Last Scheduled Contact

Any new SAEs or IREs reported to the investigator which occur **after the last scheduled contact** and are determined by the investigator to be reasonably associated with the use of the IMP, should be reported to the sponsor. This may include SAEs or IREs that are captured on follow-up telephone contact or at any other time point after the defined trial period. The investigator should follow SAEs or IREs identified after the defined trial period and continue to report any significant follow-up information to the sponsor until the events are resolved or stabilized, or the subject is lost to follow-up or has died.

6 Pharmacokinetic/pharmacogenomic Analysis

The PK samples will be analyzed for centanafadine (EB-1020) and its metabolite(s) concentrations. Times postdose will be determined from the date and time of first pill captured by AiCure for the dose prior to the PK sample and the sampling date and time captured in the eCRF; for the sample taken 7 days after the last dose of IMP (Day 49 for completers), the date and time of the first pill from last dose taken (on Day 42 for completers) will be used as the date and time of the dose prior to the sample. No formal statistical comparisons are planned. A separate population or PK/pharmacogenomic modeling may be performed using the data from this trial and other trials.

7 Statistical Analysis

7.1 Sample Size

The primary efficacy endpoint is the change from baseline at Day 42 in AISRS total score. The trial will compare the placebo arm to the centanafadine dose arms, randomized at a ratio of 1:1:1, with an overall alpha of 0.05 for the primary endpoint.

Based on the results at various dose strengths from phase 2 centanafadine trials, it is reasonable to expect a treatment difference of 5 points with a standard deviation (SD) of 12.5 in the mean change from baseline to Day 42 on AISRS total score in either the 200 mg TDD or 400 mg TDD arms. The planned sample size of 405 evaluable subjects (135 in each treatment arm) will yield at least 90% power to detect the treatment effects at a 2-tailed significance level of 0.05. The 2-sided alpha level for the final analysis is 0.05.

A sufficient number of subjects will be enrolled and randomized to achieve approximately 405 evaluable subjects in the double-blind treatment period (ie, subjects with an AISRS total score at baseline and at least 1 subsequent AISRS total score in the

Protocol 405-201-00013

double-blind treatment period). After allowance of 10% nonevaluable subjects in the double-blind treatment period, the total number of subjects to be randomized is 450 subjects (150 subjects in each treatment arm). In order to ensure 405 evaluable subjects, the number of nonevaluable subjects will be monitored in a blinded manner on an ongoing basis during the trial. The power and sample size were obtained using the PASS 14 (2015) statistical computing software.

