Statistical Methods:	
A sufficient number of subjects will be enrolled and randomized to achieve approximately 405 evaluable subjects in the double-blind treatment period (ie, subjects with an AISRS total score at baseline and at least 1 subsequent AISRS total score in the double-blind treatment period). After allowance of 10% nonevaluable subjects in the double-blind treatment period, the total number of subjects to be randomized is 450 subjects (150 subjects in each treatment arm). In order to ensure 405 evaluable subjects, the number of nonevaluable subjects will be monitored in a blinded manner on an ongoing basis during the trial. The power and sample size were obtained using the PASS 14 (2015) statistical computing software.
 
The primary efficacy endpoint is the change from baseline to Day 42 in AISRS total score. The estimand for the primary efficacy analysis is the difference in outcome improvement if all subjects tolerated and adhered to their treatment. This approach is Estimand #3, recommended by the 2010 National Academy of Sciences' National Research Council report on prevention and treatment of missing data and International Council for Harmonisation E9 (R1) "Addendum to Statistical Principles for Clinical Trials on Choosing Appropriate Estimands and Defining Sensitivity Analyses in Clinical Trials". This estimand focuses on the efficacy of centanafadine (SR 200mg TDD or SR 400mg TDD) in change from the baseline in AISRS total score. The objective of this trial is consistent with the election of an efficacy rather than effectiveness estimand.

Protocol 405-201-00013

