3.3 Trial Population

3.3.1 Number of Subjects and Description of Population

A total of up to 1150 male and female subjects with current diagnosis ADHD and between the ages of 18 and 55 years, inclusive, are planned to be screened in order to randomize approximately 450 subjects to yield 292+ completers.

Subjects must meet the DSM Fifth Edition (DSM-5) criteria for ADHD (including predominantly inattentive presentation, hyperactive presentation, or combined presentation) as confirmed by the ACDS Version 1.2. To confirm that ADHD is the primary diagnosis, the Mini International Neuropsychiatric Interview (MINI) will be used to identify and exclude other psychiatric conditions which would preclude enrollment.

Subjects who are not receiving any pharmacological treatment for ADHD must have an Adult ADHD Investigator Symptom Rating Scale (AISRS) score of ≥ 28 at screening and baseline. Subjects who are receiving pharmacological treatment for ADHD at screening must have a minimum AISRS score of ≥ 22 at screening, and a score of ≥ 28 at baseline (Section 3.4.2). Subjects must washout of their current ADHD therapy, if applicable, and any prohibited medications prior to baseline (Table 4.1-1).

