The primary efficacy endpoint is the change from baseline at Day 42 in Adult ADHD Investigator Symptom Rating Scale (AISRS) total score. The trial will compare the placebo arm to the centanafadine dose arms, randomized at a ratio of 1:1:1, with an overall alpha of 0.05 for the primary endpoint.

Based on the results from Phase 2 centanafadine trials, it is reasonable to expect a treatment effect of 5 points with a standard deviation (SD) of 12.5 in the mean change from baseline to Day 42 on AISRS total score. The planned sample size of 405 evaluable subjects (135 in each treatment arm) will yield at least 90% power to detect the treatment effects at a 2-tailed significance level of 0.05.

A sufficient number of subjects will be enrolled and randomized to achieve approximately 405 evaluable subjects in the Double-blind Treatment Phase (i.e., subjects with an AISRS total score at baseline and at least 1 subsequent AISRS total score in the Double-blind Treatment Phase). After allowance of 10% non-evaluable subjects in the Double-blind Treatment Phase, the total number of subjects to be randomized is 450 (150 in each treatment arm). In order to ensure 405 evaluable subjects, the number of non-evaluable subjects will be monitored in a blinded manner on an ongoing basis During the trial. The power and sample size were obtained using the PASS 14 (2015) statistical computing software.

5 Data Sets for Analysis and Missing Data

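### The claimed 90% power assumes complete Day 42 data and a single comparison; at the plan's own 292 completers neither dose reaches it, and 200 mg misses it even without dropout

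*Protocol*

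**What the plan says.** Protocol 7.1 expects the same effect for each dose: "it is reasonable to expect a treatment difference of 5 points with a standard deviation (SD) of 12.5". Subjects are "randomized at a ratio of 1:1:1", "with an overall alpha of 0.05 for the primary endpoint". It concludes that "The planned sample size of 405 evaluable subjects (135 in each treatment arm) will yield at least 90% power to detect the treatment effects", tested "at a 2-tailed significance level of 0.05". SAP section 4 repeats that 135 per arm "will yield at least 90% power to detect the treatment effects at a 2-tailed significance level of 0.05".

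The synopsis and Protocol 7.1 define evaluable as "subjects with an AISRS total score at baseline and at least 1 subsequent AISRS total score in the double-blind treatment period". A Day 42 score is not required. The only loss allowed for is 10% nonevaluable: 450 × 0.90 = 405.

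Protocol 3.3.1 plans screening "in order to randomize approximately 450 subjects to yield 292+ completers". The Trial Duration entry of the synopsis gives approximately 292.

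The primary endpoint is the Day 42 change in AISRS total score, analysed by MMRM on observed cases (Protocol 7.3.1, SAP 8.1.1). Protocol 7.3.2.1 and SAP 8.2 both use a fixed sequence starting with 400 mg on AISRS. In the SAP, 200 mg on AISRS comes second. In the protocol it comes third, after 400 mg on CGI-S. Neither sample-size section mentions the completer forecast, missing Day 42 scores or the sequence.

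**The concern.** The power calculation describes a simpler trial than the one planned, in two separate ways.

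- **Missing Day 42 data.** The forecast leaves 405 − 292 = 113 evaluable subjects without a Day 42 score. The MMRM recovers part of that information from earlier visits, but not all of it. This affects both doses.
- **The fixed sequence.** The 400 mg test comes first at full alpha and loses nothing. The 200 mg test takes place only after 400 mg has succeeded, so its power is a joint probability, below 90% even with complete data.

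The protocol assumes the same effect in either arm and speaks of treatment effects in the plural, so a reader will take 90% to cover both doses. Anyone interpreting a non-significant 200 mg result, or planning a similar trial from this one, would misjudge the risk of failure that was accepted.

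**Working it through.** **Inputs.** From Protocol 7.1: difference 5, SD 12.5, two-sided alpha 0.05, 135 per arm. From the synopsis and 3.3.1: 292 completers of 450, so 292/450 = 64.9%, 292/3 = 97.3 per arm, and 292/405 = 72.1% of evaluable subjects. Between-visit correlations and dropout timing are not in the plan. They are assumed below and shown as ranges.

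**1. The plan's own figure.** The noncentrality is 5 / (12.5 × √(2/135)) = 3.286. The noncentral t gives 90.6% power (normal approximation 90.8%). By the noncentral t, 133 per arm gives 90.15% and 132 gives 89.93%. The stated figure reproduces, with a margin of two subjects per arm.

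**2. 400 mg, completers only.** With 97.3 per arm the noncentrality is 2.790 and power is 79.3% (normal approximation 79.7%). This is a lower bound, because the MMRM also uses earlier visits.

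**3. 400 mg, MMRM.** The number observed per arm falls in equal steps over the six visits: 135, 127.5, 119.9, 112.4, 104.9, 97.3. For each dropout pattern, the inverse covariance of the observed visits is multiplied by the number of subjects in that pattern, and the results are summed. Inverting the sum gives the variance of the Day 42 mean. Effective n is the single-subject Day 42 variance divided by that variance. Power uses the noncentral t at SD 12.5. The last column is explained in step 4.

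| Between-visit correlation | Effective n per arm | Power, 400 mg | Power, 200 mg in SAP order |
|---|---|---|---|
| constant 0.4 | 104.9 | 82.2% | 72.3% |
| constant 0.5 | 108.4 | 83.4% | 74.0% |
| constant 0.7 | 116.9 | 86.1% | 77.8% |
| constant 0.8 | 122.1 | 87.6% | 79.9% |
| as in STAT-4.1.1 | 118.0 | 86.4% | 78.3% |

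The STAT-4.1.1 matrix comes from the trial's results, so it serves only as a check on plausible correlations. Its implied correlations of Days 7 to 35 with Day 42 are 0.49, 0.70, 0.80, 0.86 and 0.87.

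A wider search used correlations of 0.3 to 0.9, constant or first-order autoregressive, with early, even or late dropout. It gave about 80% to 89.5% for 400 mg (normal approximation). No scenario reached 90%. Reaching it needs an effective n of about 131.4 per arm, which means recovering (131.4 − 97.3)/(135 − 97.3) ≈ 90% of the missing information.

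**4. 200 mg through the sequence.** The two test statistics share the placebo arm, so with equal arms their correlation is 0.5. Power is the bivariate normal probability that both exceed 1.96:

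- no missing data (n = 135): 84.4%;
- completers only (n = 97.3): 68.3%;
- MMRM with even dropout: 72.3% to 79.9%, as in the table.

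Under the protocol order 400 mg must also succeed on CGI-S first. That cannot raise 200 mg power. Its cost cannot be calculated, because no CGI-S effect or SD is given.

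**The case against.** The best defence is that the arithmetic is right. As the power of one comparison with complete data, 90% is correct, and neither document says in so many words that 200 mg has 90% power after the 400 mg gate. That stands: the fault lies in the assumptions behind the figure, not in the calculation.

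The 400 mg shortfall depends on correlations and dropout timing that the plan does not state, and in the most favourable case tried it is only about half a point. It also depends on the SD. If 12.5 is an unadjusted SD and the model's covariates reduce it to about 11.8, effective n 118.0 gives 90.0% for 400 mg. The STAT-4.1.1 residual variance of 117.05 (SD 10.82) gives 94.2% for 400 mg and 90.2% for 200 mg in sequence. But that SD was known only after the trial and cannot support a planning claim, and the sample-size sections claim no gain from adjustment. At SD 11.8, 200 mg in sequence is still 83.6%.

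Protocol 3.3.1 writes 292 with a plus sign, which may mean a minimum. The synopsis, however, also gives approximately 292, and the calculation applies at that number. If early terminators count as completers under the Day 42/ET wording of Protocol 3.10, there would be fewer true Day 42 scores.

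**Conclusion.** The concern holds. At the plan's SD of 12.5 and its forecast of 292 completers, neither dose has 90% power.

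- **400 mg:** about 82% to 88% under the MMRM with even dropout and constant correlation 0.4 to 0.8, with 79% as the completers-only lower bound. The shortfall comes only from missing Day 42 data.
- **200 mg:** 84% with complete data, a result that needs no dropout or between-visit correlation assumption, and about 72% to 80% with the expected dropout in the SAP order. The protocol order can give no more than this.

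The 200 mg conclusion is the firmer of the two. The 400 mg conclusion rests on assumed correlations and dropout timing, but every scenario tried at SD 12.5 stayed below 90%.

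**What to change.** Keep the sample size, endpoint and analysis. Replace the single power sentence in the synopsis, Protocol 7.1 and SAP section 4 with a statement for each dose. For example: with about 35% of randomized subjects lacking a Day 42 score (1 − 292/450 = 35.1%), power under the MMRM is about 82% to 88% for 400 mg versus placebo and about 72% to 80% for 200 mg versus placebo within the fixed sequence.

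Alongside it, state the assumed dropout pattern and between-visit correlations, whether SD 12.5 is before or after covariate adjustment, and that 90% refers to one comparison with complete Day 42 data. If the sponsor has its own correlation or dropout assumptions, those should replace the illustrative ranges here.

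The protocol and SAP testing orders must also be reconciled, because the 200 mg figure depends on which applies. If the protocol order is kept, a CGI-S effect and SD are needed to state it.

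The cost is wording only. The stated power becomes less favourable, and no data collection or analysis changes.
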